Abbreviated Title: RFA + TACE with RO Beads

Version Date: 04/13/2018

Abbreviated Title: RFA + TACE with RO Beads

CC Protocol #: 16-CC-0049 C

NCI Version Date: 04/13/2018

NCT Number: NCT02649868

A Phase II Study using LC Bead LUMI Radio-Opaque Embolic Beads to Detect and Characterize the Vascularity of Hepatic Tumors during Treatment with Transarterial Embolization (TAE) Alone or combined with Thermal Ablation

NIH Principal Investigator: [name].

Director, Center for Interventional Oncology

Diagnostic Radiology Department (DRD)

National Institutes of Health (NIH)

[name]

[name]

[contact]

Email: [contact]

Device:

Device Name:	LC bead LUMI Radiopaque embolic beads
FDA 510(k) Clearance:	K152157
Manufacturer:	BTG

Abbreviated Title: RFA + TACE with RO Beads

Version Date: 04/13/2018

PRÉCIS

Background:

- Hepatocellular Carcinoma (HCC) is the 3rd most common cause of cancer globally with an increasing incidence worldwide.
- Management of hepatic malignancies from primary Hepatocellular Carcinoma (HCC) or metastatic disease involves a multidisciplinary approach of surgery and chemotherapy and in the case of HCC, transplant, anti-VEGF sorafenib, or local or regional image guided therapies.
- Thermal ablation (RFA or MWA) and transarterial embolization (TAE) are minimally invasive image guided local or regional therapies that have been extensively studied for decades, and more recently and to a lesser extent have been studied together as a combination therapy.
- LC Bead LUMITM, a radiopaque embolic bead product (company code BTG 13-002), is an imageable spherical embolic product that can be visualised by X-ray based imaging (e.g., fluoroscopy and CT).
- The beads are non-resorbable microspheres with calibrated size ranges that occlude arteries for the purpose of blocking the blood flow to a target tissue.
- LC Bead LUMITM are intended to be used for the embolization of hypervascular tumors and arteriovenous malformations (AVMs).

Objectives:

- To determine the imaging characteristics of radiopaque beads including qualitatively comparing virtual and actual bead perfusion in the treatment of hepatic tumors using bead embolization.

Eligibility:

- Treatment eligibility for TAE requires agreement between the Interventional Radiologist reviewing imaging and feasibility of TAE and the patient's NIH primary treatment team who will evaluate the patient's clinical parameters to undergo anesthesia and the TAE and or ablation procedure.
- At least ≥ 18 years of age
- Patients with pathologically proven, hepatic-dominant neoplasm.
- The extent of hepatic metastases is $<50\%$ of total hepatic volume.
- Past treatment with Y90 must be 6 months from TAE treatment and liver function within NIH institutional limits
- ECOG performance status ≤ 2
- Patients must have normal organ and marrow function per laboratory parameters
- Patients with minor allergies to iodine will also be excluded.

Design:

- Number of Participants: 30

Abbreviated Title: RFA + TACE with RO Beads

Version Date: 04/13/2018

- Recruitment Time Frame: ~2 years
- Type of Study: Feasibility study
- This is a pilot study to assess the characteristics of radio-opaque bland beads during TAE in the treatment of hepatic malignancies. Patients may also receive thermal ablation treatment in conjunction with TAE if clinically indicated, although comparison of bead treatment with or without thermal ablation is not part of the study's aim.
- To compare virtual and actual perfusion characteristics of the LUMI radiopaque beads with CBCT and/or CT. Patients' scans will be obtained per TAE standard of care schedule. Other imaging evaluation of this therapy may be performed at regular intervals following completion of treatment, and will be governed by standard conventional imaging regimen post treatment.
- The choice of which combination of imaging (CT, Cone beam CT (CBCT), or fluoroscopy) and when to image, will be made by the clinical care team for the patient, based upon multidisciplinary recommendations and NIH Clinical Center customary use and standard of care, and will be purely clinical decisions (not research-related).
- The participants will have a diagnosed hepatic malignancy, and be eligible to undergo transarterial embolization and thermal ablation under general anesthesia. The LC LUMI bead will be used in the transarterial embolization procedure.
- Follow up will continue for 12 months from the time of initial treatment.
- Patients will be evaluated in multidisciplinary GI medical oncology clinic and up to 30 patients will be enrolled to accrue 20 evaluable patients.

TABLE OF CONTENTS

PRÉCIS.....	3
TABLE OF CONTENTS	5
1 INTRODUCTION	8

1 INTRODUCTION

1.1 STUDY OBJECTIVES

1.1.1 Primary Objective

To determine the imaging characteristic of radiopaque beads including qualitatively comparing virtual and actual bead perfusion in evaluating tumor vascularity in the treatment of hepatic tumors using bead embolization.

Commented [WA([1]): Moved to statistical section as this is more of another way to measure the primary objective. Will need SRC approval as another primary objective.

1.2 BACKGROUND AND RATIONALE

Management of hepatic malignancies from primary Hepatocellular Carcinoma (HCC) or metastatic disease involves a multidisciplinary approach of surgery and chemotherapy and in the case of HCC, transplant, anti-VEGF sorafenib, or local or regional image guided therapies. The less invasive approaches of transarterial embolization (TAE) or ablation with thermal energy (radiofrequency or microwave) are options that can be palliative or curative. Each approach has its potential for complications that are modest in comparison to surgery.

Treatment of hepatic malignancies with TAE or ablation alone often requires multiple courses because tumor margins are not well delineated by current imaging. Defining tumor locations during the course of an ablation or TAE may enhance accuracy and ability to devascularize the tumor and ultimately causing tumor death. BTG and NIH have collaborated to create a radiopaque bead called LC LUMI bead. These are investigational radiopaque, biocompatible, non-resorbable beads manufactured to be visible under multiple modes of imaging (fluoroscopy, CT, and cone beam CT). BTG PLC International and its subsidiary UK company, Biocompatibles developed the LC Lumi bead under a CRADA with the NIH, and LC Lumi bead is manufactured by BTG PLC, an international specialty pharmaceutical company that is developing and commercializing products targeting critical care, cancer neurologic and interventional medicine. The FDA has granted BTG a 510 (k) Clearance for the LC LUMI beads on December 11, 2015 (see Appendix A, Section 12.1)

Hepatocellular Carcinoma (HCC) is the 3rdth most common cause of cancer globally with an increasing incidence worldwide [1]. In countries that lack systemic screening for cirrhotic patients, 50-70%, are diagnosed with advanced stage, symptomatic HCC [2]. Liver tumors have historically responded poorly to systemic chemotherapies and radiation, while < 30% are candidates for surgery or transplantation due to inadequate functional liver reserve at advanced disease [3]. In recent years, minimally invasive procedures have been shown effective for certain patients who do not qualify for surgical resection. Thermal ablation (RFA or MWA) and embolization (TAE) are minimally invasive image guided local or regional therapies that have been extensively studied for decades, and more recently and to a lesser extent have been studied together as a combination therapy. The use of TAE without chemotherapy (vs. TACE = with chemotherapy). Thermal ablation and TAE (or TACE) have been used separately or together as acceptable treatments for focal malignancies in the liver [4-7]. Local and regional therapies may provide benefits in comparison to traditional cancer treatments, with reduced morbidity and mortality, can be performed on an outpatient basis, repeated over time, and used in conjunction with other cancer treatments [8].

Metastatic cancer to the liver is common from primary liver cancer, neuroendocrine tumors, colorectal, lung, and urogenital cancers (adrenal, kidney, and bladder) and are treated with embolization and or ablation, often with the goal of debulking of palliation.

Abbreviated Title: RFA + TACE with RO Beads

Version Date: 04/13/2018

Thermal ablation and TAE attack different components of the tumor and can work synergistically to create an additive effect of treatment, potentially resulting in a more robust response.

Thermal ablation treats the center or “inside” of the tumor, potentially leaving behind a viable hypervasculär margin sub-lethally treated secondary to the “heat sink effect” [9-11]. This hypervasculär margin on the “outside” of the tumor is the target of embolization which targets and embolizes the vasculature, potentially eliminating this viable margin [12, 13].

RFA and MWA produce tissue death through hyperthermic injury. Coagulation necrosis occurs from an alternating high frequency electric current in the radiofrequency range (460-500 kHz). This is delivered via an electrode placed directly in the target lesion and the movement of ions within the tissue creates frictional heat as the ions try to follow the alternating current [14]. RFA is currently the most common ablative therapy, recommended for lesions ≤ 3 cm (single or up to 3 lesions) and single lesions ≤ 5 cm who are not candidates for liver resection or liver transplant, but have preserved liver function [7]. This results in very narrow indications. The major limiting biological factor to thermal ablation is hepatic blood flow. The body temperature blood in adjacent tumor blood vessels is relatively cooler than the ablation zone, leading to conduction of thermal energy away from the target tissue and into the blood. The result is limited heating of perivascular tissue and subsequent irregularly shaped treatment spheres of ablation [10, 15]. This “heat sink” effect results in sparing of tumor cells nearest the blood vessels, with subsequent tumor regrowth. Given this phenomenon, different methods of hepatic blood flow reduction, and direct treatment of perivascular cells with regional chemotherapy have been developed, including TACE or DEBs.

MWA uses electromagnetic energy creating a rapid and homogeneous heating of tissue and subsequently coagulation necrosis. Another mechanism of MWA function is ionic polarization with conversion of kinetic energy into heat. A more homogeneous, larger ablation zone that is easily predicted is feasible and the heat- sink effect is attenuated. One reason for the reduced heat-sink effect may be the faster heating and higher temperatures provided by microwave energy. Notably, the ablation heat beyond the microwave field is conducted in a similar way as in RFA with the heat- sink effect still present. Another consequence of the different production of heat seen with MWA is that the time needed for ablation is less in MWA than that required in RFA.

Transcatheter arterial embolization is a standard treatment option for patients with unresectable primary hepatocellular carcinoma (HCC) and is used to treat some liver metastases. Despite the widespread use and success of embolization for more than three decades, there remains a lack of consensus regarding optimal technique. For example, there is variability in (i) type and size of embolic agent, (ii) use of chemotherapeutic agent(s), (iii) degree of catheter selectivity, and (iv) optimal embolization endpoint. This material and technical variability may be perpetuated by a lack of knowledge concerning the influence of these embolization variables on patient outcomes. Educated recommendations to standardize material choice and procedural technique may be formulated if embolic material and drug locations inside the embolized tissue were known with a high degree of confidence.

Although extensive experience has been accumulated for both RFA and TACE or DEBs for the treatment of a variety of liver tumors, the reoccurrence rates of liver lesions treated with each alone have been reported to be quite high, largely depending upon patient selection and size and

Abbreviated Title: RFA + TACE with RO Beads

Version Date: 04/13/2018

number of lesions. Since each treatment attacks the tumor in different ways, it could potentially be more effective than either alone.

Studies in the literature have already implemented combination therapy of RFA and TACE or DEBs and shown it to be both feasible and safe [1, 16-19]. These studies have thus far shown improved progression free survival with tumors $\geq 3\text{cm}$ with combination therapy as compared to RFA alone. They have also shown that overall survival is improved with tumors $> 5\text{cm}$, and that combination therapy is comparable to RFA alone along all tumor sizes [16, 18, 20]. Although these studies have shown combination therapy to be safe and feasible, there is currently no standard convention for how to most effectively combine the two. Studies have completed TACE followed by RFA same day, 1 week or up to 3 to 4 weeks after the initial procedure. Other studies have performed RFA followed by TACE. Coming to a conclusion of overall effectiveness from these varying protocols is challenging and more studies are needed to assess a standard convention.

Additionally, subject treated with Y90 at least 6 months prior to treatment and meet all other eligibility requirements will be eligible. These subjects were ineligible initially due to concerns of Y90 induced hepatic dysfunction and uncertainty of LUMI LC beads additive effects.

1.2.1 Virtual Perfusion

Another factor during treatment of HCC and liver metastases with TAE is the ability to accurately determine the vessels for embolization and to effectively perfuse the selected vessels with beads during the procedure. Limited tumor vascularity and overlapping vessels can pose a challenge in determining the ideal location necessary for embolization with beads. EmboGuide a FDA-approved software medical device, will be used to assist the physician performing the procedure by having the functionality to analyze tumor vascularity, and the capability to identify and annotate the feeding vessels intended for embolization. The software will enable comparison for the actual and virtual perfusion characteristics of LUMI beads during embolization.

1.2.2 LC Bead LUMI™

LC Bead LUMI™, a radiopaque embolic bead product (company code BTG 13-002), is an imageable spherical embolic product that can be visualized by X-ray based imaging (e.g., fluoroscopy, CBCT, and CT). The beads are non-resorbable microspheres with calibrated size ranges that occlude arteries for the purpose of blocking the blood flow to a target tissue. LC Bead LUMI™ are intended to be used for the embolization of hypervascular tumors and arteriovenous malformations (AVMs).

1.2.3 Summary and Rationale

LC Bead™ microspheres are indicated for embolization of hypervascular tumors and have been commonly used for embolization of liver tumors. Certain hepatic-dominant hypervascular neoplasms may be treated with minimally invasive image guided therapies ablation and transarterial embolization. In the past, LC beads were not made visible on x-rays, therefore the physician was unable to visualize the exact location of the beads. Lumi beads are basically LC beads with iodine, so they can be visualized on x-ray or CT, and show the physician where the beads are going. Characterizing the bead appearance on x-ray, fluoroscopy, and CT could inform future treatments by identification of tumor at risk for under-treatment, which may also help targeting for further treatment (sometimes with RFA), or for follow up.

2 ELIGIBILITY ASSESSMENT AND ENROLLMENT

2.1 ELIGIBILITY CRITERIA

Patients will be screened for this study only after the patient has been determined eligible for the TAE procedure by the referring/ primary team and an interventional radiologist.

2.1.1 Inclusion Criteria

- 2.1.1.1 Patients who are determined to be eligible for TAE by an interventional radiologist and the primary/referring team will be eligible for the study.
- 2.1.1.2 Patients with pathologically proven hepatic-dominant neoplasm that might otherwise be candidates for standard clinical TAE.
- 2.1.1.3 Extent of hepatic metastases is <50% of total hepatic volume.
- 2.1.1.4 At least ≥ 18 years of age: Because it is exceeding rare for someone under the age of 18 to develop hepatocellular carcinoma, we will exclude patients <18 years of age, children are excluded from this study, but will be eligible for future pediatric trials.
- 2.1.1.5 ECOG performance status 0-2

Six months since last treatment with Y90

- 2.1.1.6 Patients must have normal or adequate organ and marrow function as defined below:

	Laboratory tests	Inclusion Criteria
Hematology	Absolute Neutrophil Count	$> 1500 / \text{mm}^3$ without help of Filgrastim or other stimulating growth factors
	Platelet Count	Patient eligible if platelet count is correctable to $\geq 50,000/\text{mm}^3$
	Hemoglobin	Patient eligible if hemoglobin count is correctable to $\geq 8.0 \text{ g/dl}$
Serum Chemistry	ALT/AST	≤ 5 times the upper limit of normal; except in the presence of obstructive liver metastases where ALT/AST may be up to 10 times the upper limit of normal
	Creatinine	$< 1.5 \times$ institution upper limit of normal OR creatinine clearance $\geq 45 \text{ mL/min}/1.73 \text{ m}^2$ for patients with creatinine levels above institutional normal.
	Total Bilirubin	$\leq 3 \text{ mg/dl}$
	Prothrombin Time	within 2 seconds of the upper limit of normal (INR ≤ 1.8)

- 2.1.1.7 Ability of subject to understand and the willingness to sign a written informed consent document.
- 2.1.1.8 Evidence of post-menopausal status or negative urinary or serum pregnancy test for female pre-menopausal patients. Women will be considered post-menopausal if they have been amenorrheic for 12 months without an alternative medical cause.

2.1.2 Exclusion Criteria

- 2.1.2.1 No contraindications to receive iodine products.

Abbreviated Title: RFA + TACE with RO Beads

Version Date: 04/13/2018

- 2.1.2.2 Main Portal Vein Occlusion or other contraindications to chemoembolization
- 2.1.2.3 ~~Prior selective internal radiation therapy (SIRT) with 90-Y of more than one treatment per lobe or a single whole liver treatment less than 6 months from proposed treatment.~~
- 2.1.2.4 Patients taking immunosuppressive drugs or unable to come off of ongoing chronic anticoagulation will not be eligible.
- 2.1.2.5 Uncontrolled intercurrent illness including, but not limited to, ongoing or active infection with systemic manifestations, symptomatic congestive heart failure, unstable angina pectoris, cardiac arrhythmia, or psychiatric illness/social situations that would limit compliance with study requirements.
- 2.1.2.6 Pregnant women and nursing mothers are excluded from this study because of the potential for teratogenic or abortifacient effects of required multiple imaging and associated radiation doses, anesthesia and risks during thermal ablation to the fetus. Enrolled patients must agree to use adequate contraception (hormonal or barrier method of birth control; abstinence) prior to study entry and for the duration of study participation. Should a woman become pregnant or suspect she is pregnant while she is participating in this study, she should inform her treating physician immediately.

Commented [GC([2]): Can we delete this? We will need a justification for removal.

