9.1.2 Justification for Exclusion

Patients that are pregnant will be excluded from this trial because of concern that ionizing radiation may be harmful to the developing fetus. Patients with altered mental status that prevents consent or answering questions will be excluded. Patients with uncorrectable coagulopathies may be at increased risk for bleeding, and will be excluded. Patients with multiple co-morbidities, sepsis, or multiple high-risk medical problems may be at increased risk for morbidities or mortalities, and will be excluded. This does not change standard transarterial embolization exclusions.

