9.5 EVALUATION OF BENEFITS AND RISKS/DISCOMFORTS AND RISKS/BENEFITS ANALYSIS

The risks inherent to this device itself should be identical to the risks of undergoing the clinically indicated procedure, and are outlined in detail below. This use of beads for embolization has been standard therapy for liver tumors for decades. The LUMI bead is very similar in composition to the widely used over the last decade and commercially available LC bead™. The LUMI LC bead is basically an LC bead with attached iodine to make it visible on x-rays, like regular iodine contrast. The risks of these LUMI LC beads are discussed in the table below:

No	Potential Hazard	Resultant Harm	Risk Evaluation Discussion	Mitigation Strategy
1	Transarterial embolization Thermal ablation	
• Pain• Bleeding• Infection• Nausea• Anesthesia complications• Pneumothorax• Liver abscess formation• Acute cholecystitis• Gastric ulceration• Pancreatitis• Misembolization• Radiation Injury• Allergic reactions to anesthesia medications• Allergic reaction to intravenous contrast• Liver failure• Stomach ulcer• Postembolization syndrome (24-72 hours following chemoembolization, during hospital	The LC beads will be placed using standard of care transarterial embolization protocol. The tumor site is accessed via an inguinal artery	Pre-operative clearance from the anesthesia service. Pain and Palliative care consult as clinically indicated Evaluation of any outstanding cardiology, pulmonology or other co-morbid disease states before IR procedures; routine general sedation and peri-operative, antiemetics, antacids, antibiotics, local anesthesia and post operative patient controlled analgesia, bedrest, nursing surveillance and antibiotics. Patients with known contrast allergies will be pretreated per standard of care Patient with known allergies to any anesthesia agents will receive comparable anesthesia medications that they can tolerate Peri-procedure imaging to evaluate immediate LC bead placement enhanced by the beads radiopaque element will allow immediate visualization

No	Potential Hazard	Resultant Harm	Risk Evaluation Discussion	Mitigation Strategy

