		
observation period)
 
 • Abdominal visceral injury (from non-target embolization, 1-2 weeks following embolization): 		
of misembolization.
 
Patient are admitted to the inpatient hospital ward during the immediate post-operative period and monitored.
 
Post-operative changes in patient comfort vital signs or diagnostics such as liver enzymes will prompt further evaluation.

2	LC Lumi beads	Allergic Response	The preclinical experience does not raise concerns that the radiopaque LC beads produces any known acute allergic response (see Investigator's Brochure).	Patient with known allergy to LC beads or its components will be excluded from the study
3	LC Lumi beads	Endotoxin adverse reaction	The preclinical experience does not raise concerns that the radiopaque LC beads produces any known acute endotoxin response (see Investigator's Brochure).	
Labeled non-pyrogenic Endotoxin testing in animal models proved no change in temperature during an observation period following injection of extracted LC bead LUMI.
 
Acutely febrile patients will be excluded from the procedure as is standard of care

4	LC Bead LUMITM Bead	Genotoxicity, Carcinogenicity, reproductive toxicity	The preclinical experience does not raise concerns that the radiopaque LC beads produces any known genotoxicity, carcinogenotoxic or reproductive toxic adverse events (see Appendix C, Section 0)	Patients who are of reproductive age will be counseled on use of adequate birth control. All women who are of reproductive age and are not sterile or post-menopausal will be tested for pregnancy prior to all imaging.
5	LC Bead LUMITM beads	Systemic or local toxicity	The preclinical experience does not raise concerns that the radiopaque LC beads produces any known acute systemic or local adverse response (see Appendix C, Section 0)	Patient are admitted to the inpatient hospital ward during the immediate post-operative period and monitored. Post-operative changes in patient comfort, physical exam, vital signs or diagnostics such as liver enzymes will prompt further evaluation with imaging and immediate treatment.

Abbreviated Title: RFA + TACE with RO Beads

Version Date: 04/13/2018

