10 DEVICE INFORMATION

10.1 LC BEAD LUMI™

(Also refer to the Investigational Brochure and the LUMI™ Bead Technical Dossier for complete information)

LC Bead LUMI™ consist of a macromer derived from a sulphonate modified polyvinyl alcohol (PVA) macromer and a sulphonated cross-linking agent (AMPS = 2-Acrylamido-2-methylpropane sulphonate, sodium salt), which contains a radiopaque moiety (triiodobenzyl

Abbreviated Title: RFA + TACE with RO Beads

Version Date: 04/13/2018

entity) that is covalently bound within the hydrogel structure. The radiopaque moiety is derived from triiodobenzyl aldehyde. The incorporation of this radiopaque moiety into the co-polymer imparts X-ray imageability by rendering the beads radiopaque.

Multiple sizes are available for the product LC Bead LUMI™. Glass vials in all size ranges will contain approximately 2ml of product in around 6 – 7 ml physiological buffered saline. The total volume in the vial is 8 - 9 ml. Each vial is provided sterile (SAL 10⁻⁶) via moist heat sterilization and is only intended for single use.

The product is mixed with non-ionic contrast agent, such as Omnipaque™ (not included with the product) to help the physician / radiologist to evaluate the human vascular supply and in order to monitor the delivery of the product during the embolization procedure. LC Bead LUMI™ will be delivered using a typical microcatheter commercially available to the Interventional Radiologist community in 2.4 to 4 Fr (French size) ranges. The physician will use the product to administer the beads intra-arterially in order to physically block the target vessel.

LC Bead LUMI™ has been designed as a radiopaque version of the LC Bead™. Currently embolization with LC Bead™ lacks post-procedural imaging feedback on exact bead location. The embolization process with LC Bead™ is monitored by detecting changes in antegrade flow of soluble iodinated contrast in which the beads are diluted. The embolization is continued until a desired embolization endpoint is reached. This process is completed without specific feedback on the bead location. In order to address this limitation, BTG has developed an imageable spherical embolic bead that can be visualized by X-ray based imaging (e.g., fluoroscopy and CT). The potential benefits envisaged for such a line extension are listed below:

- The radiopaque product will embolize the tumor feeding vessels, providing a marker for the location of the tumor.

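### The protocol gives conflicting rules for iodine and contrast allergy, and the inverted exclusion criterion 2.1.2.1 does not settle which one applies

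*Combined protocol and SAP*

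**What the plan says.** Four protocol statements bear on whether a patient with an iodine, contrast or bead allergy may be treated.

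- **Précis, Eligibility:** "Patients with minor allergies to iodine will also be excluded". The rule refers to iodine and reaches even minor allergy.
- **Section 2.1.2, criterion 2.1.2.1:** "No contraindications to receive iodine products", placed under the heading for exclusions.
- **Section 9.5, risk table row 1 (embolization and ablation):** the harms include "Allergic reaction to intravenous contrast", and the mitigation is "Patients with known contrast allergies will be pretreated per standard of care".
- **Section 9.5, risk table row 2 (the bead):** "Patient with known allergy to LC beads or its components will be excluded from the study". This exclusion appears nowhere in section 2.1.2.

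Around these, criterion 2.1.2.2 adds only a general clause, "Main Portal Vein Occlusion or other contraindications to chemoembolization". Section 9.1.2 justifies the exclusions without mentioning allergy and ends with "This does not change standard transarterial embolization exclusions". Section 10.1 says of the bead: "The product is mixed with non-ionic contrast agent". Under Cautions, the instructions for use in Appendix C advise against the bead where the patient is hypersensitive to contrast agents. Among potential complications they list allergic reactions in patients sensitive to iodine.

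**The concern.** A screener who finds a contrast allergy in the history has no single rule to follow. The Précis, if it covers contrast, says exclude. Row 1 says premedicate and proceed. The instructions for use advise against the device. The criterion that should decide is written backwards and is silent on the kind and degree of allergy.

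This is a matter of safety and of consistent eligibility. The beads do not resorb, so the exposure cannot be withdrawn after a reaction. Section 4.1.3 collects allergic reactions to the bead only from grade 3 upward, so milder reactions in premedicated patients could go unrecorded. Two screeners could also decide differently on the same patient, each citing the protocol.

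**Working it through.** No formula applies, because the point depends on no rate, power or error level. The check sets the statements side by side.

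| Place | Allergy addressed | Direction |
|---|---|---|
| Précis, Eligibility | Iodine, including minor | Exclude |
| 2.1.2.1 | Contraindication to iodine products | Inverted; intent presumably to exclude; degree not stated |
| 9.5, row 1 | Contrast | Pretreat, hence treat |
| 9.5, row 2 | Bead or components | Exclude |
| Appendix C, Cautions | Contrast | Advises against the bead |

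1. **Do row 1 and the exclusions concern different patients?** Row 1 covers the procedure and row 2 the bead, so one might premedicate for contrast and exclude only for bead allergy. At treatment the exposures are not separate. Section 10.1 has the bead mixed with contrast, section 10.1.2 (step 8) prepares it in undiluted non-ionic contrast, and the Appendix C caution links contrast hypersensitivity directly to use of the bead.

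2. **Does the conflict need iodine allergy and contrast allergy to be the same thing?** No. If the Précis is set aside entirely, row 1 and the Appendix C caution still give opposite directions for the same patients.

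3. **Does correcting the polarity of 2.1.2.1 resolve it?** No. A criterion excluding patients with a contraindication to iodine products would still leave open whether a contrast allergy that can be premedicated is a contraindication. That is exactly where the Précis and row 1 part.

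4. **Does another provision decide?** Section 3.2 places embolization under both the device instructions and the institution's standard of care, without ranking them. On this question the two point in different directions, since row 1 itself describes pretreatment as the standard of care. Criterion 2.1.2.2 is too general to help.

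5. **Counts.**
   - Protocol statements: 2 exclude (Précis, row 2) + 1 pretreats (row 1) + 1 inverted (2.1.2.1) = 4.
   - Live criteria in 2.1.2: 2.1.2.1, 2.1.2.2, 2.1.2.4, 2.1.2.5 and 2.1.2.6 = 5, since 2.1.2.3 is struck through. Of these, 0 name allergy or hypersensitivity.
   - Groups justified in 9.1.2: pregnancy; altered mental status; uncorrectable coagulopathy; multiple co-morbidities, sepsis or other high-risk problems = 4. Of these, 0 concern allergy.

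**The case against.** The strongest reply has four parts.

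- **Terms.** Iodine allergy and contrast allergy are different terms, and the protocol never says that one includes the other. That is true, and it limits the conflict between the Précis and row 1. It leaves the conflict between row 1 and the instructions for use untouched.
- **Authority.** A generic mitigation line in a risk table is not an eligibility rule, and no one would apply 2.1.2.1 literally in a trial of an iodinated bead. Both points are fair. But the intended reading of 2.1.2.1 does not settle the question, so the risk table is the only place in the protocol body that says what to do with a contrast-allergic patient.
- **Section 3.2.** Requiring the device instructions together with the standard of care can be read as requiring both, which would make the caution binding. This reading leans protective. However, the caution is a recommendation and not one of the listed contraindications, so it does not clearly override a named pretreatment practice.
- **Safeguards.** The primary team and an interventional radiologist must both find the patient eligible (sections 2.1 and 2.2), and the research team reviews the history and physical (section 2.2.1). These checks reduce the risk. But screening for embolization follows ordinary clinical practice, and nothing tells the screeners which allergy rule governs.

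The counts also need care. The bead-allergy line in row 2 contradicts nothing, and section 9.1.2 does not claim to be exhaustive. They show where the rule is missing; they do not measure the harm.

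**Conclusion.** The concern holds. The protocol excludes even minor iodine allergy in one place and plans to pretreat contrast allergy in another, and the exclusion criterion that should decide is inverted and, once corrected, still silent. Following row 1 as written would treat patients for whom the device instructions advise against the bead.

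That core conflict rests only on row 1, the Appendix C caution and the delivery of the bead in contrast. The further conflict with the Précis assumes that its iodine rule reaches contrast. The number of patients affected is unknown, because no prevalence is given. The enrolment of 30 and the target of 20 evaluable patients do not depend on the point, and no analysis changes. It should be corrected for safety and consistent eligibility; it does not threaten the validity of the results.

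**What to change.** Reword 2.1.2.1 as a positive exclusion, for example: *any contraindication to, or known allergy or hypersensitivity (including minor) to, iodine, iodinated contrast, or LC Bead LUMI or its components*. Amend the pretreatment line in section 9.5, row 1, so that it no longer implies enrolling these patients. This follows the direction already taken by the Précis, row 2 and the device instructions, and it brings the bead-allergy exclusion into the operative list.

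If the sponsor prefers to keep premedicated contrast-allergic patients eligible, that is also coherent. It should then say so in 2.1.2, narrow the Précis rule and justify departing from the Appendix C caution. Either way, section 2.1.2 must state one rule.

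The cost is two short wording edits by amendment. The downside is that some contrast-allergic patients, of unknown number, become ineligible. Sample size and analysis stay as they are.
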